6.1 Inclusion Criteria

- 1. Male or female aged 18-75 years.
- 2. BMI between 25 Kg/m2 to 40Kg/m2, or waist circumference between 88cm to 200cm for women, and between 102cm to 200cm for men. If there is deviation above the upper limit, please consult the MRI center, to ensure that the machine is suitable for the patient.
- 3. Known type II Diabetes Mellitus or pre-diabetes according to American Diabetic Association. One of the following 3 criteria is needed for pre-Diabetic: Fasting Plasma Glucose > 100mg/dl (5.5 mmol/l) or 2hPG following 75g OGTT >140 mg/dl (7.8 mmol/l) or HbA1c > 5.7%. HbA1c can be repeated at Investigator's discretion.
- 4. Histologically proven Steatohepatitis on a diagnostic liver biopsy performed either during screening or within 6 months before screening visit, confirmed by central laboratory reading of the slides (steatosis ≥1 + inflammation ≥1 + ballooning ≥1). total activity NAS score of 4 or more

- 5. Liver fat concentration of 5.5% or more as measured by NMRS.
- 6. Biopsies with an activity NAS score of 4 or more.
- Normal synthetic liver function (serum albumin >3.2g/dl, INR 0.8-1.2, conjugated bilirubin < 35 μmol/L).
- 8. Understanding the nature of the study and signature of the written informed consent.
- 9. Negative pregnancy test at study entry for females of child bearing potential.
- 10. Females of child bearing potential practicing reliable contraception throughout the study period (including oral contraceptive). If barrier methods are used, it is recommended to practice two methods (e.g. male condom + female diaphragm with spermicide). For country-specific requirements (e.g. Germany) contraception failure rates (Pearl Index) should be under 1% in accordance with the recommendations of the CTFG Working Group on Contraception.
- 11. Hypertensive patients must be controlled by stable dose of anti-hypertensive medication for at least 2 months prior to screening.
- 12. Patients previously treated with vitamin E (>400IU/day), Polyunsaturated fatty acid (>2g/day), Ursodeoxycholic acid or fish oil can be included if drugs are stopped at least 3 months prior to diagnostic liver biopsy (and are not started during the trial). These treatments-dosages are allowed if they were stable for at least 12 months prior to biopsy and can remain stable throughout the study. (Dosages less than the amounts stated above are allowed without washout- or stable-period restrictions.)

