- Treatment with Valproic acid, Tamoxifen, Methotrexate, Amiodarone or chronic treatment with anti-cholinergic agents, corticosteroids, high dose estrogen and tetracycline within 12 months prior to the screening visit.
- 19. Chronic treatment with antibiotics (e.g. Rifaximin).
- 20. Homeopathic and/or alternative treatments. Any treatment should be stopped during the screening period at least 48 hours before randomization.
- 21. Uncontrolled hypothyroidism defined as Thyroid Stimulating hormone >2X the upper limit of normal (ULN). Thyroid dysfunction controlled for at least 6 months prior to screening is permitted.
- 22. Patients with renal dysfunction eGFR< 40.
- 23. Unexplained serum creatine phosphokinase (CPK) >3X the upper limit of normal (UNL). Patients with a reason for CPK elevation may have the measurement repeated prior to randomization; a CPK retest > 3X ULN leads to exclusion.
- 24. Patients with condition(s) that makes them unsuitable to perform the NMRS (as determined by the PI or the MRI facility).
- 25. Known Hypersensitivity to Aramchol or to any of the excipients in the tablets
- 26. Known Hypersensitivity to cholic acid or bile acid sequestrants

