12.9.2 Laboratory Data

Analyses of safety central laboratory data will be performed in the following manner:

• The below table displays the quantitative criteria used to define the potentially clinically significant (PCS) abnormal laboratory values. Measurements used in the analysis are those taken only at post randomization day visits. The incidence tables of PCS lab values as well as the individual subject listing will be provided. Please note that the denominator to be used for calculating percentages is the number of subjects with at least one post randomization day observation.

Test Group	Parameter	Lower Normal SI	Upper Normal SI	Lower PCS	Upper PCS
Chemistry	ALBUMIN (g/L)	32	55		<30g/l
Chemistry	ALK PHOS (U/L)	29	149		>2.5ULN
Chemistry	ALT (U/L)		45		>3ULN
Chemistry	AST (U/L)		41		>3ULN
Chemistry	CALCIUM (mmol/L)	2.14	2.62	<2mmol/l	>2.9mmol/l
Chemistry	CHOLESTEROL (mmol/L)	2.2	5.2		>7.75mmol/l
Chemistry	CPK (U/L)	26	145		>2.5ULN
Chemistry	CREATININE (umol/L)	31	106		>1.5ULN
Chemistry	GGT (U/L)	2	42		>2.5ULN
Chemistry	GLUCOSE, PLASMA (mmol/L)	3.9	6.9	<3.0mmol/l	>13.9mmol/l
Chemistry	POTASSIUM (mmol/L)	3.5	5.3	<3.5mmol/l	>5.5mmol/l
Chemistry	SODIUM (mmol/L)	135	148	<130mmol/l	>150mmol/l
Chemistry	TOTAL BILIRUBIN (umol/L)	2	21		>1.5ULN
Coagulation	APTT (secs)	22	35		>1.5ULN
Coagulation	INR	0.8	1.2		>1.5ULN
Hematology	HEMOGLOBIN (g/L)	113	156	<100g/l	
Hematology	PLATELETS (x10E9/L)	140	370	<75 x10e9 /L	
Hematology	WBC (x10E9/L)	3.5	10.5	<3.0 x 10e9 /L	>100 x 10e9 /L

Criteria for Potentially Clinically Significant Laboratory Values

ULN=upper limit of normal range.

• The incidence (no. of subjects) of abnormal values at any time after randomization day, calculated for subjects with normal values at baseline will be provided. Analysis will include, per tested parameter, those subjects with normal baseline and at least one post-randomization

day measurements. Summary table will display the number and relative percentage of subjects with at least one abnormal value (above upper and below the lower normal range) at any time post randomization days.

- Quantitative laboratory measurements were categorized with reference to the normal ranges as Low, Normal or High. Shift analysis of the categorical change form baseline to each scheduled visit and to the last observed value will be provided. Please note that the last measurement per visit will be used to represent subject's value in the analysis in case of sporadic repeated measurement within a visit.

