- Box-Plots of measurements done, figures of mean values ±SEs of changes from baseline as well as descriptive statistics for all laboratory quantitative parameters and changes from baseline will be provided by scheduled visits and treatment groups. Please note that the last measurement per visit will be used to represent subject's value in the analysis in case of sporadic repeated measurement within a visit.
- Evaluation of Drug-Induced Serious Hepatotoxicity (eDISH, Drug Saf 2011; 34 (3): 1-10) was performed according to the following:
 - ✓ Pre-study drug administration data was not included in the analysis.
 - ✓ Max ALT was defined as the maximal value of all ALT assessments measured after randomization.
 - ✓ The maximal Bilirubin (Total) value taken for the scatter plot was selected among measurements taken at the same day or after the maximum ALT value was detected.

The eDISH figure, list of subjects with potential drug-induced serious hepatotoxicity according to this analysis, summary table of the incidence of subjects falling within each of the 4 quadrants will be provided. For subjects falling within the Cholestasis and Hy's Law

Quadrants an additional individual subjects listings will be generated displaying demographics, exposure and termination reason, concomitant drug use, adverse events and selected laboratory data.

• The distribution of maximal values of AST, ALT and total bilirubin at any time after randomization day in term of the upper normal range multiples will be provided for subjects with normal AST, ALT and total bilirubin at baseline.

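### The tables of potentially clinically significant (PCS) laboratory values ignore baseline, so for CPK, bilirubin, ALT, AST and GGT they mix abnormalities present at entry with new ones

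*Combined protocol and SAP*

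**What the plan says.** Section 12.9.2 sets quantitative PCS limits by parameter and plans incidence tables and subject listings.

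- **Numerator:** "Measurements used in the analysis are those taken only at post randomization day visits".
- **Denominator:** "the denominator to be used for calculating percentages is the number of subjects with at least one post randomization day observation".
- **Example limits:** "CPK (U/L) 26 145 >2.5ULN" and "TOTAL BILIRUBIN (umol/L) 2 21 >1.5ULN". ALT and AST are PCS above 3 times the upper limit of normal (ULN), and GGT above 2.5 times.

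The entry criteria that bear on the same parameters are:

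- Section 6.2, exclusion 23: "Unexplained serum creatine phosphokinase (CPK) >3X the upper limit of normal".
- Section 6.1, inclusion 7: "Normal synthetic liver function (serum albumin >3.2g/dl, INR 0.8-1.2, conjugated bilirubin < 35" umol/L.
- Sections 6.1 and 6.2 set no upper limit for ALT, AST, GGT or total bilirubin.

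Three other outputs in section 12.9.2 take account of baseline category:

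- incidence of out-of-range values among subjects normal at baseline;
- shift tables ("Quantitative laboratory measurements were categorized with reference to the normal ranges as Low, Normal or High");
- the distribution of maximum AST, ALT and total bilirubin in ULN multiples, which "will be provided for subjects with normal AST, ALT and total bilirubin at baseline".

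**The concern.** A PCS table is normally read as a count of abnormalities that arose on treatment. Here a subject who entered past a limit and stays past it counts as a case although nothing has changed. The population has steatohepatitis, and change in ALT is a key secondary endpoint, so raised enzymes at entry are to be expected.

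The parameters affected are ones a safety reader will look at first. Section 3.1.5 reports a minor transient transaminase rise in rats that was not reproduced. Section 7.4 reports a model-predicted 1.9-fold rise in simvastatin exposure at 600 mg, and statins at a stable dose are permitted. If old and new abnormalities are pooled, a real excess of new ones looks smaller in relative terms, and chance differences between arms at baseline carry into the table. The vital-signs PCS table in section 12.9.3 does include change-from-baseline criteria; the laboratory table has none.

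**Working it through.** **Step 1. Compare the PCS limits with the entry limits.** ULN values come from the section 12.9.2 table. I assume the same ULN applied at screening.

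| Parameter | PCS limit | Entry limit | Can a subject be PCS at entry? |
|---|---|---|---|
| CPK | 2.5 × 145 = 362.5 U/L | 3 × 145 = 435 U/L | Yes, 362.5 to 435 |
| Total bilirubin | 1.5 × 21 = 31.5 umol/L | conjugated < 35; total not capped | Yes |
| ALT | 3 × 45 = 135 U/L | none | Yes |
| AST | 3 × 41 = 123 U/L | none | Yes |
| GGT | 2.5 × 42 = 105 U/L | none | Yes |
| Albumin | < 30 g/L | > 32 g/L | No |
| INR | 1.5 × 1.2 = 1.8 | 0.8 to 1.2 | No |

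**Step 2. Follow a subject who starts between ULN and the PCS limit** (for example ALT between 45 and 135 U/L) and then crosses it. The two baseline-normal tables leave this subject out. The shift table shows High to High. The PCS table counts the subject, but together with those past the limit at entry. For CPK and GGT there is a further gap: the maximum-value table does not cover them, and the baseline-normal table counts any value out of range. So no table isolates a new PCS crossing even from a normal baseline.

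**Step 3. Illustrate the size.** The documents give no PCS rate, so there is no planned figure to reproduce. Let q be the share past the limit at baseline, s the share of those with a PCS value again after randomisation, and e the rate of new PCS values among the rest.

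Table rate = q·s + (1 − q)·e

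If s is the same in both arms, the risk difference is (1 − q)·(e_active − e_placebo) whatever s is. All values of q, s and e below are assumptions.

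| e: placebo, active | q | s = 1: rates (ratio) | s = 0.5: rates (ratio) | Difference, points |
|---|---|---|---|---|
| 2%, 8% (ratio 4.0; 6.0 points) | 5% | 6.9% v 12.6% (1.83) | 4.4% v 10.1% (2.30) | 5.7 |
| | 10% | 11.8% v 17.2% (1.46) | 6.8% v 12.2% (1.79) | 5.4 |
| | 20% | 21.6% v 26.4% (1.22) | 11.6% v 16.4% (1.41) | 4.8 |
| 2%, 15% (ratio 7.5; 13.0 points) | 5% | 6.9% v 19.3% (2.8) | 4.4% v 16.8% (3.8) | 12.4 |
| | 10% | 11.8% v 23.5% (2.0) | 6.8% v 18.5% (2.7) | 11.7 |
| | 20% | 21.6% v 32.0% (1.5) | 11.6% v 22.0% (1.9) | 10.4 |

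**Step 4. Noise from baseline.** With 96 subjects on a dose and 48 on placebo (section 12.1), the standard deviation of the chance difference in baseline share is √[q(1 − q)(1/96 + 1/48)]. This is 3.9, 5.3 and 7.1 points at q = 5%, 10% and 20%. At full persistence and q = 10% it is about as large as the 5.4-point difference in the 2% v 8% case.

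**Step 5. Unequal persistence.** If the drug also normalised some raised values, s would differ by arm. With assumed s = 0.8 on placebo and 0.5 on active, q = 20% and e of 2% and 8%:

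- placebo: 0.2 × 0.8 + 0.8 × 0.02 = 17.6%
- active: 0.2 × 0.5 + 0.8 × 0.08 = 16.4%

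The table would then point the other way from the new events. This shows what can happen; it is not a forecast.

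**The case against.** The case against is substantial, and much of it stands.

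- **Other outputs give cover.** Section 12.9.2 also plans descriptive statistics and changes from baseline by visit and arm for all quantitative parameters, with no restriction to baseline-normal subjects. It adds individual PCS listings and an eDISH analysis of maximum ALT with bilirubin. Section 12.7.5 models change in ALT adjusted for baseline. Worsening of an existing condition can be an adverse event (section 11.1) and would appear in the section 12.9.1 tables. A reader might infer that a harm signal in subjects with raised baselines would go unseen; the documents do not support that. The cover is partial, however. Means can hide a few large rises, listings are not incidence by arm, and eDISH leaves out pre-drug values. Adverse-event reporting depends on investigator judgement and has a carve-out for expected disease worsening.
- **Timing.** A reader might infer that a subject who is PCS at entry becomes a case at the first on-drug visit. Section 12.9.2 analyses central-laboratory data, and weeks 2, 4, 8 and 40 may be tested locally (sections 8.2.4 and 10.2). Week 24 is the first on-treatment visit fixed to the central laboratory.
- **Size.** The dilution in the ratio depends on persistence, and the risk difference shrinks only by the factor (1 − q). A loss of statistical power might also be inferred, but section 12.9.2 contains no test.
- **Unseen text.** Section 12 refers to a separate SAP that gives more detail and prevails. It can be said only that the text available contains no such table.

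**Conclusion.** The point holds for CPK, total bilirubin, ALT, AST and GGT. For these, the planned PCS incidence combines abnormalities present at entry with new ones, and no laboratory incidence table in the text isolates new crossings by subjects who start above normal. It does not extend to every limit, since entry criteria keep out subjects past the albumin and INR limits. The CPK overlap is a narrow band.

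No single figure for the effect can be defended, because q and its persistence are not in the documents. What follows without knowing them is the direction: under common persistence the risk difference shrinks by (1 − q), the ratio is diluted more, and baseline imbalance adds noise. Only descriptive safety tables are affected. The primary analysis, the type I error control and data collection are untouched, so this is a cheap improvement and not a threat to the trial's conclusions.

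The WBC upper limit is a separate matter. At 100 × 10e9/L it is 100/10.5 = 9.5 times the upper normal value, while the other upper limits in the table are at most 3 times theirs. It has no bearing on the baseline question.

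**What to change.** In section 12.9.2:

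1. Add a treatment-emergent PCS incidence for each parameter, with numerator and denominator both restricted to subjects who are not past the same limit at baseline and have a post-randomisation value.
2. Show by arm how many subjects were already past each limit at baseline.
3. For ALT, AST, GGT, CPK and bilirubin, among subjects above ULN at baseline, show by arm the distribution of the maximum post-randomisation value as a multiple of the subject's own baseline.

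If the separate SAP already contains these outputs, a cross-reference is enough. The cost is SAP wording and a few lines of programming on data already collected, slightly smaller denominators and one extra table.

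Separately, the sponsor should check the WBC upper limit and reconcile it with the other rows or explain it.

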12.9.3 Vital Signs

Vital signs will be analyzed in the following manner:

• The below table displays the quantitative criteria used to define the potentially clinically significant (PCS) abnormal values. Measurements used in the analysis are those taken post randomization day. The incidence tables of PCS values as well as the individual subject listing will be provided. Please note that the denominator to be used for calculating percentages is the number of subjects with at least one post randomization day observation.

Potentially Clinically Significant (PCS) Vital Signs Ranges

Parameter	Criteria for PCS		
High BP (mmHg)	SBP > 160 or DBP > 100		
Low BP (mmHg)	SBP < 80 or DBP < 50		
Change from Baseline in BP (mmHg)	SBP > 30 or DBP > 30		
Heart Rate (Beats/Min)	< 50 or > 120		
Change from Baseline in Heart Rate (Beats/Min)	≥ 30		

• Box-Plots of measurements done, figures of mean values ±SEs as well as descriptive statistics for all parameters and changes from baseline will be provided by scheduled visits and treatment groups. Please note that the last measurement per visit will be used to represent subject's value in the analysis in case of sporadic repeated measurement within a visit.

12.9.4 12-Lead ECG

The study site Investigator classified each ECG as either "normal", "abnormal not clinically significant (NCS)", or "abnormal clinically significant (CS)".

Analyses of ECG evaluations will be performed in the following manner:

- Distribution of the number of subjects by the interpretation outcome made by the Investigator by treatment group and scheduled visit.
- Shift analysis of categorical change of Investigator assessment to each scheduled visit and to last observed assessment will also be performed.
- Incidence and listings of individual subjects ECG findings of Potential Clinical Significance (PCS) following randomization date and onwards will be provided.

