7.4 Drug interactions

No drug interaction studies have yet been performed. A simulation PBPK fit for purpose model predicted increased exposure to drugs that are substrates for CYP3A4 metabolism when administered concomitantly with Aramchol. The interaction ratios for both AUC0-24 and Cmax were 1.3 for midazolam and 1.9 for simvastatin in the presence of Aramchol 600 mg. Investigators should note that Aramchol may cause an increase in plasma concentrations of some statins (e.g. simvastatin, lovastatin). Therefore, caution should be exercised in treating patients receiving such highly susceptible substrates and other CYP3A4 substrates with narrow therapeutic range such as alfentanil, fentanyl and cyclosporin. No significant interaction potential was observed with the CYP2B6 and BCRP substrates.

Studies have shown that, while Aramchol does not undergo extensive metabolism, CYP3A4 activity does contribute to the clearance of Aramchol, which could therefore be affected by inducers or inhibitors of CYP3A4. To ensure adequate exposure to Aramchol, co-administration (for more than 3 consecutive days) of enzyme inducers such as rifampicin, carbamazepine, phenytoin, enzalutamide and St John's wort should be avoided. Conversely, concentrations of Aramachol could be increased in the presence of strong CYP3A4 inhibitors. To avoid such interactions, co-administration of clarithromycin, verapamil, diltiazem, itraconazole and most other conazole antifungal agents, ciprofloxacin, grapefruit juice and a number of anti-HIV agents e.g. ritonavir, should be used with caution if required.

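### The change-from-baseline vital-sign criteria in section 12.9.3 state no direction, so large falls that stay above the low-level limits are either left unflagged or pooled with rises

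*Combined protocol and SAP*

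**What the plan says.** The PCS table in section 12.9.3 has two kinds of criterion. Its inequality signs are underlined, so they mean at least and at most.

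- **Levels, given in both directions.** High pressure is "SBP > 160 or DBP > 100" and low pressure is "SBP < 80 or DBP < 50". Heart rate is flagged at 50 or below and at 120 or above.
- **Changes, given as one inequality.** The row that begins "Change from Baseline in BP (mmHg" carries the criterion "SBP > 30 or DBP > 30". The row that begins "Change from Baseline in Heart Rate (Beats/Min" carries a limit of 30 or more. Neither row has a plus or minus sign, an absolute-value sign, or a word for increase or decrease.

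The table feeds an incidence table of PCS values and a listing of individual subjects, using post-randomization measurements. Separately, the section says that "descriptive statistics for all parameters and changes from baseline will be provided by scheduled visits and treatment groups", together with box plots and figures of means.

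**The concern.** Change from baseline is ordinarily later value minus baseline. A programmer who applies a limit of 30 or more to that quantity counts rises and nothing else. The level rows in the same table look both ways, so the change rows may have been meant to do so too, but the text does not say.

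Neither reading gives a good safety table. If the rows are signed, a large fall is counted only when it ends at or below a low-level limit. If they are absolute, an arm with *r* subjects who rise and *f* others who fall shows the same count, *r* + *f*, as an arm with *f* who rise and *r* who fall. Opposite effects would then look alike. Two programmers could produce materially different tables from the same data and both claim to follow the plan.

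**Working it through.** The plan states no expected frequency for these criteria, so there is no figure to reproduce. The check has three steps.

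**1. Example profiles put through the rows.** Each line considers one measure alone.

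| Measure | Baseline to later | Change | Change row, signed | Low-level row | Change row, absolute |
|---|---|---|---|---|---|
| SBP | 150 to 110 | −40 | no | no (110 > 80) | yes |
| SBP | 115 to 85 | −30 | no | no (85 > 80) | yes |
| SBP | 110 to 80 | −30 | no | yes | yes |
| DBP | 85 to 52 | −33 | no | no (52 > 50) | yes |
| DBP | 80 to 50 | −30 | no | yes | yes |
| Heart rate | 110 to 55 | −55 | no | no (55 > 50) | yes |

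A fall of 30 is sure to meet a low-level row only if baseline SBP is at most 80 + 30 = 110, baseline DBP at most 50 + 30 = 80, or baseline heart rate at most 50 + 30 = 80.

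**2. How much the reading changes the count.** The 240 subjects come from section 6. Section 5.1 has vital signs taken at every visit, so visits 3 to 11 give nine post-randomization readings. The SD of change is not in the documents; 12, 15 and 18 mmHg are assumed for SBP, with mean change 0 and correlation 0.5 between changes at different visits. Per visit:

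- Signed: P(change ≥ 30) = 1 − Φ(30/SD). For SD 12, 1 − Φ(2.5) = 0.62%; for SD 15, 1 − Φ(2) = 2.3%; for SD 18, 1 − Φ(1.67) = 4.8%.
- Absolute: twice that, 1.24%, 4.6% and 9.6%.

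At least one flag over nine visits, by simulation of 400,000 subjects, with expected numbers out of 240:

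| SD of SBP change | Signed | Absolute |
|---|---|---|
| 12 | 4.1% (9.8) | 8.1% (19.5) |
| 15 | 12.5% (29.9) | 24.8% (59.6) |
| 18 | 22.5% (54.0) | 44.6% (107.2) |

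By symmetry, the share with a fall of 30 or more equals the signed column. That is the group the change row omits on the signed reading.

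**3. How many falls the low-level rows pick up.** Baselines are again assumed, and each measure is taken alone at a single visit.

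- SBP mean 130, SD 14, SD of change 12 to 18: 0.3% to 0.4% of falls of 30 or more end at 80 or below.
- DBP mean 80, SD 9, SD of change 8 to 12: 3.2% to 4.0% end at 50 or below.
- Heart rate mean 75, SD 10, SD of change 10: 17.1% end at 50 or below.

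Counted per subject over nine visits, with an assumed within-subject SBP SD of 10 to 11, about 3% to 4% of subjects with an SBP fall of 30 or more also have some SBP reading of 80 or below. On these assumptions the low-level rows recover few of the falls.

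**The case against.** The best defence is that the row is undirected, so an absolute reading is at least as natural as a signed one and would flag every fall in the table above. The subject listing would then let a reader see the direction. Other parts of the plan also look at falls: signed changes are summarised by visit and arm in section 12.9.3, section 10.5 sends significant findings that meet the definition to the adverse-event record, section 12.9.1 tabulates those events, and section 18.2.4 has the medical monitor review individual data. Section 12 adds that the SAP signed on 26Jan2017 prevails, and it may define the sign. The shares in the working assume no drug effect, so they describe chance excursions, equal in all arms, not a missed signal.

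Most of this stands, and it keeps the point small. It does not remove it. Visit-level means describe group shifts and do not count individuals with large excursions, which is what the incidence table is for. An absolute reading still pools the two directions in that table.

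Three stronger readings might be inferred, and the documents do not support them.

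- *Large falls can never be flagged.* The rows for low pressure and for heart rate of 50 or below catch falls that reach those levels, and an absolute reading catches the rest.
- *The shared 30 mmHg limit makes the diastolic criterion almost idle.* That depends on an SD the documents do not give. For an assumed SD of diastolic change of 8, 10 or 12, a rise of 30 or more occurs at least once over nine visits in about 0.1%, 1.0% or 4.1% of subjects, or 0.2, 2.4 or 9.8 of 240. The row is also a composite that can be met through systolic pressure. The documents give no basis for another limit.
- *The interaction section makes a fall in pressure an expected effect.* Section 7.4 says a model "predicted increased exposure to drugs that are substrates for CYP3A4 metabolism when administered concomitantly with Aramchol", and inclusion criterion 11 reads "Hypertensive patients must be controlled by stable dose of anti-hypertensive medication for at least 2 months prior to screening". But section 7.4 names no antihypertensive among the affected substrates; verapamil and diltiazem appear as inhibitors that could raise Aramchol. No passage predicts hypotension, and the point does not rely on it.

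**Conclusion.** The point holds as a gap in specification. Section 12.9.3 does not say whether its change criteria are signed or absolute. The signed reading leaves unflagged those falls that stay above 80 mmHg systolic, 50 mmHg diastolic or 50 beats/min; the absolute reading merges rises with falls. The choice about doubles the expected count by chance alone. This ratio follows from symmetry of changes around zero, while the percentages rest on assumed SDs, an assumed correlation of 0.5 and nine visits.

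The importance is minor. One descriptive safety table and its listing are affected, and nothing in the efficacy inference, the control of type I error or the sample size depends on it. If the separately signed SAP already fixes the sign, the ambiguity goes, but a single row would still either omit falls or pool them with rises.

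**What to change.** In section 12.9.3, define change as post-randomization value minus baseline. Replace each change row by two: 'increase from baseline of 30 or more' and 'decrease from baseline of 30 or more'. Tabulate them by arm, separately for SBP, DBP and heart rate. A subject who meets both counts once in each. Show the direction in the PCS listing as well. Keep the 30-unit limits as they are; no change to the diastolic limit is proposed.

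The cost is six change rows in place of two, so four more rows in one table, and a small programming change.
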